CRO	Contract Research Organization
DCC	Data Coordinating Center
DHHS	Department of Health and Human Services
DMID	Division of Microbiology and Infectious Diseases, NIAID, NIH
DSMB	Data and Safety Monitoring Board
eCRF	Electronic Case Report Form
FDA	Food and Drug Administration
FWA	Federalwide Assurance
GCP	Good Clinical Practice
HIPAA	Health Insurance Portability and Accountability Act
ICF	Informed Consent Form
ICH	International Conference on Harmonisation
IDS	Investigational Drug Services
IEC	Independent or Institutional Ethics Committee
IND	Investigational New Drug Application
IRB	Institutional Review Board
MERS-CoV	Middle East respiratory syndrome coronavirus

МОР	Manual of Procedures
Ν	Number (typically refers to subjects)
NIAID	National Institute of Allergy and Infectious Diseases, NIH
NIH	National Institutes of Health
OCRA	Office of Clinical Research Affairs, DMID, NIAID, NIH, DHHS
OHRP	Office for Human Research Protections
OHSR	Office for Human Subjects Research
ORA	Office of Regulatory Affairs, DMID, NIAID, NIH, DHHS
РНІ	Protected Health Information
PI	Principal Investigator
SAE	Serious Adverse Event
SOP	Standard Operating Procedure
US	United States
WHO	World Health Organization

[figure not shown]
Summary

Full Title:	Pre-exposure prophylaxis for coronavirus: A Pragmatic Randomized Clinical Trial	
Short Title:	PREP COVID-19	
Clinical Phase:	III	
Sponsor:	Investigator-Initiated Protocol, University of Minnesota	
Principal Investigators:	[name]	
Accrual Ceiling	3500	
Study Population	Healthcare workers at high risk for exposure to COVID-19 cases	
Objective	Test if pre-exposure prophylaxis with hydroxychloroquine can prevent development of COVID-19 disease	
Study Design	Double-blind, randomized clinical trial Internet-based trial driven by self-report. Study medicine delivered by courier to consented participants.	
Intervention Arms:	 Hydroxychloroquine 200mg tablet. 1. 400 mg orally once, followed by 400mg 6 to 8 hours later, thereafter 400mg weekly for the duration of follow up, up to 12 weeks 2. 400mg orally once, followed by 400mg 6 to 8 hours later, thereafter 400mg twice weekly for the duration of follow up, up to 12 weeks 	
Control Arm:	Placebo 2 tabs once, followed by 2 tabs 6 to 8 hours later, thereafter two tabs weekly or twice weekly for the duration of follow up, up to 12 weeks	
Primary Endpoint	COVID-19-free survival	

Secondary Endpoints	 Incidence of confirmed SARS-CoV-2 detection Incidence of possible COVID19 symptoms Incidence of all-cause study medicine discontinuation Ordinal Scale of COVID-19 Disease maximum severity if COVID-19 diagnosed Incidence of Hospitalization for COVID-19 or death Incidence of study medication-related side effects 	
Duration of Participation	• Recruitment and follow up will be internet-based. All patients will be followed for at least 4 weeks. Recruitment is expected to take 4 weeks, for a total study duration of 8 weeks. But the total study duration will depend on the actual rate of enrollment. Study drug will be given for a maximum of 12 weeks.	
Inclusion Criteria	 Healthcare worker, at high risk of COVID-19 exposure: Persons primarily working in emergency departments (physicians, nurses, ancillary staff, triage personnel) Persons primarily working in intensive care units (physicians, nurses, ancillary staff, respiratory therapists) Persons performing aerosol generating procedures: ex. Anesthesiologists, nurse anesthetists (CRNAs) First responders: ex. EMTs, paramedics 	
	 Age >=18 years of age Provision of Informed Consent 	
Exclusion Criteria	 Active COVID-19 disease Confirmed prior COVID-19 disease Current fever, cough, shortness of breath Contraindication or allergy to chloroquine or hydroxychloroquine Prior retinal eye disease Known Chronic Kidney disease, Stage 4 or 5 or dialysis. Known glucose-6 phosphate dehydrogenase (G-6-PD) deficiency. Weight <40 kg Current use of hydroxychloroquine or cardiac medicines of flecainide, amiodarone, digoxin, procainamide, or propafenone Current use of medications with known significant drug-drug interactions: artemether, lumefantrine, mefloquine, tamoxifen, or methotrexate. 	

Statistical	 10% transmission rate for high-risk healthcare workers with		
Assumptions	no treatment		
	 Alpha = 0.025 (to account for two treatment groups vs. placebo comparisons) Assuming 15% lost to follow up in the placebo group and 5% lost to follow up in each treatment group N=3500 has 80% power to detect a hazard ratio of 0.65, using a two-sided log-rank test 		

Schematic of Study Design:

At the close of the study, any participant with ongoing illness will continue to be assessed for up to a total of 90 days after the common closing date.

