3.2.2 Secondary Outcome Measures

- Incidence of confirmed SARS-CoV-2 detection
- Incidence of symptoms compatible with COVID19 (possible disease)
- Incidence of all-cause study medicine discontinuation or withdrawal
- Ordinal Scale of COVID-19 Disease Severity (for those who develop COVID-19)
 - No illness
 - Illness with outpatient observation
 - Hospitalization (or post-hospital discharge)
 - Hospitalization with ICU stay or death
- Incidence of hospitalization or death
- Self-reported adherence
- Self-reported study medication side effects

Primary outcome of COVID-19-free survival will be confirmed by positive test. Assessment of other outcome measures will be primarily by self-report. As necessary, COVID-19 disease will be verified from public health records, medical records, or death certificates.

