4.3.2 Randomization

- Participants will be randomized at the investigation pharmacy
- The investigational pharmacy will dispense masked study medicine (hydroxychloroquine or placebo)
- The study medicine will be shipped to participants to arrive ~1 day after enrollment
- 4.3.3 Day 1 Virtual visit
 - Verify receipt of study medicine
 - Clinical status check-in
 - Begins taking study medicine (2 tabs), then 2 tabs in 6-8 hours
 - Query for symptom status
 - Query for hospitalization or SAEs
- **4.3.4** Weekly Virtual visit
 - Clinical status check-in for COVID-19 symptoms
 - Assessment of adherence and side effects by self-report
 - Continue study medicine up to 12 weeks
 - Query for study medicine side effects since enrollment
 - Query for SARS-CoV-2 testing
 - Query for hospitalization or SAEs
- **4.3.5** Study termination virtual visit (to be completed on or shortly after the common closing date for the study)
 - Clinical status check-in for COVID-19 symptoms
 - Query for study medicine adherence and side effects since enrollment
 - Query for SARS-CoV-2 testing
 - Query for hospitalization or SAEs
 - Query for pregnancy status
 - Final outcome assessment
- **4.4** Individually identifiable health information: Name, date of birth, and phone number will be collected so as to prescribe study medication. Email addresses will be collected for communication. If participants are hospitalized, the hospitalization date will be collected.

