8.2 Methods and Timing for Assessing, Recording, and Analyzing Safety Parameters

8.2.1 Adverse Events

Hydroxychloroquine has an excellent safety track record, being first FDA-approved in 1955. Adverse events will not be captured unless they result in hospitalization. See Serious Adverse Events below.

Expected adverse events would include normal events within the general population as well as COVID19-related disease events which may include the need for hospitalization, pneumonia, respiratory failure, sepsis, and death.

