8.2.3 Serious Adverse Events

Hospitalization or death are protocol-defined endpoints.

8.2.4 Procedures to be Followed in the Event of Abnormal Laboratory Test Values or Abnormal Clinical Findings

Not applicable

8.3 **Reporting Procedures**

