8.3.1 Serious Adverse Events

An AE or suspected adverse reaction is considered a serious adverse event (SAE) if it results in any of the following outcomes:

PREP COVID-19

- Death,
- a life-threatening adverse event (as below),
- hospitalization,
- a persistent or significant incapacity or substantial disruption of the ability to conduct normal life functions, or
- congenital anomaly/birth defect.
- Important medical events that may not result in death, be life-threatening or require hospitalizations may be considered serious when based upon appropriate medical judgment they may jeopardize the participant or subject and may require medical or surgical intervention to prevent one of the outcomes listed in this definition.
- Examples of such medical events include allergic bronchospasm requiring intensive treatment in an emergency room or at home, blood dyscrasias or convulsions that do not result in inpatient hospitalization, or the development of drug dependency or drug abuse.
- Life-threatening adverse event. An AE is considered "life-threatening" if, in the view of either the site principal investigator or sponsor, its occurrence places the subject at immediate risk of death. It does not include an AE that, had it occurred in a more severe form, might have caused death. For life-threatening AEs, subjects would be recommended /expected to be hospitalized.

Based on the known safety track record of hydroxychloroquine, this pragmatic protocol will focus on death, life-threatening AEs, and hospitalizations. Incapacity / permanent disability is a possibility with COVID19, but this is not associated with hydroxychloroquine. In the event of incapacity, the subject would be expected to be hospitalized.

Hydroxychloroquine and chloroquine are not known to cause teratogenic events and are viewed as safe in pregnancy, especially with short term use. With this trial's sample size, this will not further delineate this risk. COVID-19 disease may indeed be teratogenic. For women who are pregnant, we will ask to follow them through the end of their pregnancy.

Thus the hospitalization or death secondary endpoint will capture relevant SAEs.

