8.4 Type and Duration of Follow-up of Subjects after Adverse Events

Participants who are hospitalized for COVID-19 or SAEs will have up to 90 day follow up after the common closing date, to assess their final outcome. Management will be as per the participant's local healthcare provider.

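### The Summary limits the hospitalisation endpoint to COVID-19 while 3.2.2, 8.2.3 and 8.3.1 do not, and 8.3.1's reliance on it to capture SAEs works only for the unrestricted version

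*Combined protocol and SAP*

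**What the plan says.** The endpoint is named in four places, in two forms.

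- Summary, Secondary Endpoints: "Incidence of Hospitalization for COVID-19 or death". The admission must be for COVID-19; the death may be from any cause.
- Section 3.2.2: "Incidence of hospitalization or death", with no cause attached to the admission.
- Section 8.2.3: "Hospitalization or death are protocol-defined endpoints", again with no cause.
- Section 8.3.1 says that "this pragmatic protocol will focus on death, life-threatening AEs, and hospitalizations" and concludes: "Thus the hospitalization or death secondary endpoint will capture relevant SAEs".

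Collection is broader than the Summary endpoint. The Day 1, weekly and termination virtual visits in section 4.3 each include "Query for hospitalization or SAEs". Section 8.2.1 states: "Adverse events will not be captured unless they result in hospitalization". Section 8.4 adds: "Participants who are hospitalized for COVID-19 or SAEs will have up to 90 day follow up", counted from the common closing date.

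On analysis, 10.4 assigns Fisher's exact test by study arm to the incidence-type secondary endpoints, and 10.3 provides for descriptive reporting of secondary endpoints at interim reviews. Neither section describes a separate comparison of SAEs by arm.

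**The concern.** This endpoint does two jobs. It measures whether prophylaxis reduces serious COVID-19 illness, and under 8.3.1 it is also the trial's measure of serious harm. A COVID-19-specific count suits the first job. The second needs admissions for any cause, because a serious drug reaction would normally appear as an admission for something other than COVID-19.

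If the Summary wording is followed, the specified comparison of admissions leaves out the non-fatal events on which a drug harm would be seen. If 3.2.2 is followed, it includes them. With both definitions in the plan and neither given precedence, the choice could be made after the data have been seen. Collecting every admission does not settle which version is tested and reported by arm.

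**Working it through.** No arithmetic applies. The check is to take each kind of event through both definitions, and then to see whether another part of the plan would make the comparison that one of them omits.

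**Step 1: what each definition counts**

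| Event | Summary wording | 3.2.2 wording |
|---|---|---|
| Admission for COVID-19, participant survives | counts | counts |
| Admission for another cause, including a drug reaction, participant survives | does not count | counts |
| Admission for another cause, participant dies | counts, as a death | counts |
| Death without admission | counts | counts |

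The definitions differ in the second row only: non-fatal admissions that are not for COVID-19.

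**Step 2: which version 8.3.1 needs.** Section 8.3.1 first sets out a broad list of serious outcomes and then narrows its focus to deaths, life-threatening events and admissions. It expects participants with a life-threatening event or incapacity to be in hospital, and so concludes that the endpoint picks up what matters. Each link leads to an admission of unspecified cause. Under the Summary wording the last link fails for every event in the second row of the table. Under 3.2.2 it holds.

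**Step 3: whether another specified output fills the gap**

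- 10.4 names tests for the endpoints and for symptom severity, but none for SAEs by arm.
- 10.3 gives interim reviews the secondary endpoints descriptively, so the definition also determines what the DSMB is specified to see on this outcome.
- The progress report in 14.4 counts hospitalisations pooled over arms, so it supports no comparison.
- The ordinal severity scale in 3.2.2 has hospital categories but is for participants who develop COVID-19. If the Summary wording governs, both admission measures are restricted to COVID-19.
- The side-effect endpoint is self-reported and specifies no comparison of admissions.
- The SUSAR route in 8.3.2 concerns reporting to the IRB and FDA. It leaves out reactions already in the package insert and is not a comparison by arm.

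Under the Summary wording, then, the plan specifies no comparison by arm that includes non-fatal, non-COVID admissions.

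**Step 4: whether the data would exist.** They would. The visit queries in 4.3 ask about hospitalisation without regard to cause, 8.2.1 captures adverse events that lead to admission, and 8.4 follows participants admitted for SAEs. The gap lies in what is specified for analysis, not in what is collected.

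**The case against.** The strongest reply is that the Summary line is the outlier. The three body sections agree with one another, and 8.3.1 echoes the wording of 3.2.2, where its reasoning works. On the natural reading 8.3.1 means the 3.2.2 endpoint, and the difficulty arises only if an analyst prefers the Summary to the body. This stands as the likely intent, and it suggests which way to reconcile the text. It does not remove the conflict, because no precedence rule is given and the words added in the Summary are specific. Section 3.2.2 does not say all-cause either; that reading comes from the missing qualifier, although the protocol does use the term elsewhere, for discontinuation of study medicine.

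A second reply is that safety oversight does not hang on one endpoint. Admissions are queried at every virtual visit, SUSARs are reported, side effects form a separate endpoint and a DSMB oversees the trial. This also stands as far as collection and oversight go. None of it specifies a comparison of all admissions by arm.

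A reader might infer that the Summary version would miss every drug-related admission. The documents do not support that. Its death component is not restricted by cause, so a fatal drug-related admission counts, and non-fatal ones are still recorded even though they fall outside the endpoint.

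**Conclusion.** The conflict is real and more than clerical. One of the two definitions leaves non-fatal, non-COVID admissions out of the only comparison of hospitalisations by arm that the plan specifies outside the COVID-19 severity scale, and the stated rationale for SAE capture does not hold under that definition.

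Its reach is limited to one secondary endpoint and its descriptive use at interim reviews. The primary endpoint, alpha, power and stopping boundaries do not depend on it, and no data would be lost.

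A reader might go further and infer that a COVID-19-only count would show a benefit while the all-cause count showed a net harm. That is possible in principle, because efficacy and harm move admissions in opposite directions. The documents give no rates for COVID-19, drug-related or background admissions, however, so neither the likelihood nor the size of such a reversal can be stated.

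The conclusion rests on two readings: that the missing qualifier in 3.2.2 means any cause, and that the analyses named in 10.3 and 10.4 are the complete set specified.

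**What to change.** Define one endpoint as hospitalisation for any cause or death, reported by arm. Use the same wording in the Summary, 3.2.2 and 8.2.3, and state in 8.3.1 that this is the endpoint meant there. If the COVID-19-specific version is also wanted, list it separately as an efficacy-severity endpoint under its own name. Confirm that the any-cause version is the one tabulated by arm under 10.4 and described at interim reviews under 10.3.

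The cost is a few lines of wording and one extra table. The existing visit queries already supply the data, and the sample size is not affected.

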2 BACKGROUND INFORMATION AND SCIENTIFIC RATIONALE

2.1 Background Information

Significance of Research Question/Purpose:

Severe acute respiratory syndrome coronavirus 2 (SARS-CoV-2) is a rapidly emerging viral infection causing COVID-19. The current strategy uses a public health model of identifying infected cases, isolation, and quarantine to stop transmission. Once exposed, observation is standard-of-care.

No effective therapy currently exists for treatment. The lack of effective therapy diminishes persons presenting for self-quarantine. Having an effective pre-exposure prophylaxis for healthcare workers at high risk of contracting COVID-19, even if only partially effective, may additionally create synergy for the public health strategy of case identification and isolation – if a safe prophylaxis is available.

People who develop COVID-19 disease generally develop signs and symptoms, including mild respiratory symptoms and fever, after an average of 5-6 days after exposure (i.e. mean incubation period). The range of the incubation period is between 1 to 14 days.¹

Most people infected with the COVID-19 virus have mild disease and recover. Approximately 80% of laboratory-confirmed patients have had mild to moderate disease, which includes non-pneumonia and pneumonia cases, 14% have severe disease, and 6% are critically ill with respiratory failure, shock, and/or multiple organ dysfunction.²

Preliminary Data:

Chloroquine has *in vitro* activity in cell lines against SARS-CoV and SARS-CoV2. In a Vero E6 cell line, the half-maximal effective concentration (EC50) activity of chloroquine was 1.13 µM against SARS-CoV2.³ Hydroxychloroquine is functionally equivalent as chloroquine.

Another compound under treatment trials, remdesivir (Gilead) had an EC50 of 0.77 µM.³ Remdesivir (Gilead) is not FDA-approved and in limited quantities. Hydroxychloroquine is FDA-approved and globally is inexpensive. Chloroquine is no longer broadly available in the USA.

Existing Literature:

Several drugs, such as ribavirin, interferon, lopinavir-ritonavir, corticosteroids, have been used in patients with SARS or MERS, although the efficacy is poorly understood as a gold standard randomized clinical trial has not been conducted.

After the original 2003 SARS outbreak, screening of compounds was performed. The Special Pathogens Branch of the Division of Viral and Rickettsial Diseases at the Centers for Disease Control and Prevention (CDC) in Atlanta, Georgia investigated chloroquine.

CDC investigators reported that post-infection chloroquine treatment was effective in vitro at preventing the spread of SARS-CoV infection in an in vitro cell-based system.⁴ Vincent et al reported:

"In order to investigate the antiviral properties of chloroquine on SARS-CoV after the initiation of infection, Vero E6 cells were infected with the virus and fresh medium supplemented with various concentrations of chloroguine was added immediately after virus adsorption. Infected cells were incubated for an additional 16–18 h, after which the presence of virus antigens was analyzed by indirect immunofluorescence analysis. When chloroquine was added after the initiation of infection, there was a dramatic dose-dependent decrease in the number of virus antigen-positive cells (**Fig. 2A**). As little as $0.1-1 \mu$ M chloroquine reduced the infection by 50% and up to 90-94% inhibition was observed with 33-100 µM concentrations (Fig. 2B). At concentrations of chloroquine in excess of 1 µM, only a small number of individual cells were initially infected, and the spread of the infection to adjacent cells was all but eliminated. A half-maximal inhibitory effect (EC50) was estimated to occur at $4.4 \pm 1.0 \mu$ M chloroquine (Fig. 2C). These data clearly show that the addition of chloroguine can effectively reduce the establishment of infection and spread of SARS-CoV if the drug is added immediately following virus adsorption."4

[figure not shown]
[figure not shown]

Figure 2. Post-infection chloroquine treatment reduces SARS-CoV.

PREP COVID-19

Vincent et al also reported: "Since we observed antiviral effects by chloroquine immediately after virus adsorption, we further extended the analysis by adding chloroquine 3 and 5 h after virus adsorption and examined for the presence of virus antigens after 20 h. We found that chloroquine was still significantly effective even when added 5 h after infection (Fig. 3); however, to obtain equivalent antiviral effect, a higher concentration of chloroquine was required if the drug was added 3 or 5 h after adsorption."4

Further experiments demonstrated that chloroquine impaired the terminal glycosylation of angiotensin-converting enzyme-2 (ACE2) receptor, which is the binding site for the envelope spike glycoprotein of SARS-CoV and SAR-CoV2.

PREP COVID-19

[figure not shown]
Version 1.0 27 March 2020

Conversely, chloroquine did not have activity against Middle East respiratory syndrome coronavirus (MERS-CoV), which may be related to MERS binding to CD26 receptor protein.⁵

In a March 9, 2020 publication, hydroxychloroquine was found to have greater activity than chloroquine.⁶ The SARS-CoV-2 EC 50 values for hydroxychloroquine were 6.14 μ M at 24 hours and 0.72 μ M at 48 hours.⁶ Conversely, chloroquine EC50 values were >100 μ M at 24 hours and 18.01 μ M at 48 hours.⁶ This inhibition assay was performed with Vero cells using an infectious dose of 100 plaque forming units.

Figure 3 displays the antiviral activities of hydroxychloroquine for treatment or prophylaxis against SARS-CoV-2 *in vitro*.⁶

In a March 18, 2020 publication, hydroxychloroquine was found to be less toxic than chloroquine with slightly lower, but similar potency.⁷ At MOI of 0.01, 0.02, 0.2, and 0.8, the EC50 of

hydroxychloroquine was 4.51, 4.06, 17.31, and 12.96 μ M respectively compared to 2.71, 3.81, 7.14, and 7.36 μ M for chloroquine.

On March 20, 2020, a clinical study from France reported improved viral clearance in 20 patients treated with 600 mg per day of hydroxychloroquine for 6 days compared to 16 controls.⁸ By 6 days, 70% of those in the hydroxychloroquine group had negative viral PCR on nasopharyngeal swab compared to 13% in the control group. However, the authors noted an additional 6 subjects on hydroxychloroquine that were removed from the analysis because they did not complete therapy- 5 of these were still viral PCR positive at the time of drop-out. Without an adequately powered, randomized clinical trial, the efficacy of hydroxychloroquine against COVID-19 disease remains to be seen but these data are encouraging in regards to a potential antiviral effect.

